4.7.1.2 Deaths

Deaths will be identified from the status page, AE page, or the SAE page (with a death date, cause of death, outcome or SAE categorisation present) of the CRF. A listing of all deaths that occur will be produced for the ST+LT and Week 104 periods separately, and will present the period of occurrence. Any deaths that occur during the study will be described in depth as narratives in the CSR.

4.7.1.3 Serious adverse events

All SAEs (including hypoglycaemic and type 2 DKA events classified as SAEs) will be described in narratives, regardless of investigator assessment of causality. SAEs with an onset from Day 1 of the ST period up to and including 30 days after the last dose date in period (or up to and not including the start date of the LT period (if applicable), whichever comes first, for the ST period) will be considered as occurring during ST period. For subjects treated during the LT period, SAEs with an onset from Day 1 of the ST period up to and including 30 days after the last dose date will be considered as occurring during the combined ST+LT period. For the randomised withdrawal period, this listing will include all deaths on and after the date of withdrawal baseline until the date of Week 52 or date of last visit + 30 days (if earlier than Week 52). Number of events and incidence rates adjusted for exposure time, as described in [Section 3.4.1](#), will be reported.

The following descriptive summaries will be provided by SOC, PT and treatment group separately for the ST, ST+LT and randomised withdrawal periods:

- Any SAE
- Any SAE, up to Week 32 (ST+LT period only)
- Any SAE excluding AEs following rescue medication use (sensitivity analysis)
- Any SAE related to study drug (not related, related [including SAEs with missing relationship to study drug])
- Any SAE leading to leading to discontinuation of study medication

For the combined ST+LT period, SAEs will also be summarised by treatment group received at the time of SAE onset. For placebo subjects re-randomised to switch to dapagliflozin (or saxagliptin), SAEs will be analysed in the placebo group to the beginning of the randomised withdrawal period and in the dapagliflozin (or saxagliptin) group if the event onset occurs during the randomised withdrawal period. SAEs PTs will be presented as incidence rate adjusted for exposure, as described in Section 3.4.1.

In addition, all SAEs will also be summarised for the post-study visit at Week 104 for the Treated Subjects Data Set regardless of rescue medication initiation. For the randomised withdrawal period, subjects going through the third randomisation will be presented using the Randomised Withdrawal Subjects Data Set and will be summarised separately for the three treatment comparisons described in Section 4.1.5.

Listings of all SAEs (including pre-treatment events or post-treatment events) by subject will be provided for the ST+LT period. A separate listing will be provided for SAEs reported at the post-study visit at Week 104.

4.7.1.4 Adverse events leading to discontinuation of study medication

Adverse events with an onset during treatment for which the action taken was "drug permanently discontinued" will be summarised by SOC, PT, and treatment group for both the primary (including data regardless of rescue medication initiation) and sensitivity safety analyses (excluding data after rescue). This summary will include all hypoglycaemia events and all DKA events that are reported as SAEs and will be presented for the ST, ST+LT and randomised withdrawal periods. Note that, when summarising AEs leading to discontinuation, no upper cut-off day windows (i.e., 4 days and 30 days from last dosing date for AEs and SAEs respectively) will be applied. For ST period analyses, the only upper cut-off date will be the start date of the LT period.

A subject listing of discontinuation of study medication due to AEs will be provided for the ST+LT period.

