If a subject discontinues IP early (prior to the Week 52 visit), at the next visit the subject should be assessed according to the follow-up schedule for Early Treatment Discontinuation (ETD) (Table 5.1-4). The reason for early discontinuation must be documented in the subject's medical records and entered on the appropriate CRF page.

Subjects who discontinue IP early will still be evaluated for rescue.

After discontinuation of IP the management of the subject's diabetes will be under the care and direction of the Investigator.

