3.7.3 Discontinuation Guidelines Due to Protocol-Defined Hypoglycemia Episodes

Subjects should not be discontinued from any treatment phase based on single episodes of hypoglycemia or symptoms of hypoglycemia unless clinically indicated. The assessment of a single finger-stick or central laboratory glucose value should not be the sole assessment used to determine subject discontinuation for hypoglycemia.

Clinical indications for discontinuation of blinded study drug because of hypoglycemia may include the following:

- Multiple occasions of episodes outlined below that, in the opinion of the Investigator, indicate
 that continued treatment with study therapy is not in the best interest of the subject. This
 includes, but is not limited to:
 - Severe hypoglycemia as defined by ADA criteria.¹⁸
 - Recurrent symptoms suggestive of hypoglycemia (e.g., sweating, shakiness, increased heart rate (HR), confusion, dizziness, light-headedness, or hunger) in the absence of environmental factors known to contribute to hypoglycemia (i.e., excess physical activity, concurrent illness, or missed or delayed meal).
 - ◆ Recurrent documented capillary or plasma blood glucose values < 54 mg/dL (< 3.0 mmol/L).
- A subject may also be discontinued from the study because of severe hypoglycemia as determined by the Investigator.

Subjects who discontinue blinded study drug due to hypoglycemia will continue to be followed in line with Section 5 until death or the conclusion of the study.

Down-titration of blinded study drug and/or background antihyperglycemic agent during the study

Down-titration of blinded study drug and/or background metformin will not be allowed at any time during the study. Subjects on background insulin treatment who experience multiple or severe episodes of hypoglycemia may down-titrate insulin treatment during the study. The down-titration should be minimized, but is at the Investigator's discretion.

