5.3.1.2 Guidance on Management and Reporting of Hypoglycemia Episodes

Hypoglycemia may be an expected event in subjects who are treated for diabetes. Subjects and their family members must be aware of the possibility that hypoglycemia may occur and the

Revised Protocol No: 06

dangers associated with low blood sugar. Study subjects must be properly instructed on the recognition and management of hypoglycemia. Subjects should record in their diaries any hypoglycemic symptoms. They should be encouraged to measure, when possible, their blood glucose values when they have symptoms of hypoglycemia. Subjects should carry with them easily ingestible forms of carbohydrate at all times in order to treat an event of hypoglycemia should it occur.

During clinical trials, subjects frequently report symptoms of hypoglycemia when asked, even when treated with placebo or medications not otherwise associated with hypoglycemia. As hypoglycemia is an important event associated with diabetes therapy, all episodes which could be consistent with the clinical definition of hypoglycemia as assessed by the Investigator should be documented and reported on the appropriate eCRF page.

The Investigator is responsible for questioning the subject about all symptoms reported on the hypoglycemia portion of the diary and for determining if they meet the clinical definition of hypoglycemia. Only symptoms and/or blood glucose values deemed by the Investigator to meet the definition of hypoglycemia should be reported on the hypoglycemia eCRF pages. Signs and symptoms of hypoglycemia, hypoglycemia episode or discontinuation due to hypoglycemia should not be reported on the AE eCRF page, unless the event fulfills protocol criteria for an SAE (see Section 6.2), in which case an SAE form must be completed in addition to the hypoglycemia eCRF pages for hypoglycemia.

Hypoglycemia episodes will be classified in the Clinical Study Report (CSR) according to the ADA criteria¹⁸ and the International Society for Pediatric and Adolescent Diabetes (ISPAD) criteria.¹⁹

5.3.2 Self-Monitoring Blood Ketone Testing and Guidance on Management and Reporting of Diabetic Ketoacidosis Episodes

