3.4.1 Adverse events

AEs (serious and non-serious, excluding hypoglycaemic or DKA events that are not reported as SAEs) will be collected throughout the study up to Week 56, and will also be collected quarterly between Week 56 and Week 104 via phone assessment. Adverse events will be classified by system organ class (SOC) and preferred term (PT) according to the Medical Dictionary for Regulatory Activities (MedDRA), based on the MedDRA version current at the time of database lock. Each subject will be counted once within a SOC or PT in AE frequency tables, under the maximum intensity within each category. For summaries of AEs by relationship to study drug, as assessed by the investigator (related, not related), subjects will be counted under the most

related instance within each SOC or PT. For the summary of AEs that occurred in $\geq 5\%$ of the subjects within a treatment group (based on PTs) the number of AEs will also be presented.

Events will be considered treatment-emergent if:

- The event started on or after the first dose of IP (Day 1) and up to and including 4 days for AEs and 30 days for SAEs after the last dose date.
- The event started before Day 1 but increased in intensity or relatedness to study medication on or after Day 1.
- The event onset date is missing or partial (unless the stop date of the event indicates that the event cannot be treatment emergent).
- Events will be considered treatment emergent unless they can be proven not to be so from the data.

Details for handling of missing and partial event dates for determining treatment emergence are provided in the Appendix (Section 8.2).

Listings will include the AE duration, calculated as AE stop date - AE start date + 1. AE duration will be calculated only when complete dates (at least day, month, year) for the start and stop date are provided. Each AE will be graded for intensity (mild, moderate, severe). If intensity is missing, the event will be regarded as severe. Each AE will also be assessed for relationship to the study drug (related, not related). Adverse events with missing relationship to study drug will be considered treatment-related for the purpose of summarising AEs related to study drug. Adverse events with missing flag indicating serious will be considered serious for AE summaries.

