3.4.3.2 Hypoglycaemia

Hypoglycaemia event will not be reported on an AE CRF page unless the event fulfilled SAE criteria, in which case it should also be reported in the SAE form. Hypoglycaemic events that meet SAE criteria will be recorded as SAEs by the Investigator in the AE CRF pages. Separate pages to capture details of hypoglycaemia events are contained within the CRF. Details include symptoms, contributing factors, blood glucose measurements during the episode, date and time of last meal, third party intervention, any treatment(s) received, and whether the episode is classified as an SAE. Any self-monitored blood glucose (SMBG) measurements taken by the subjects on the days that they experience hypoglycaemia symptoms will be recorded in the CRF.

Hypoglycaemia episodes will be classified using ADA¹ and International Society of Paediatric and Adolescent Diabetes (ISPAD)² categories. Derivation details based on the information collected in the separate CRF pages for hypoglycaemia are provided in the Appendix (Section 8.9).

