4.7.1 Adverse events

4.7.1.1 All adverse events

Adverse events will be summarised as number and percentage of subjects by treatment group experiencing at least one AE within a category. Where specified, the number of events and incidence rate will also be provided. No statistical test will be performed to compare AE rates between treatment groups.

Only treatment emergent AEs with onset up to the cut-off dates defined in [Table 8](#) will be included in AE summaries. All AEs (including pre-treatment events) will be listed. Where relevant, AE listings will also include the most recent treatment dose received on or prior to AE onset.

The primary analyses of AEs will include data regardless of rescue medication initiation. Additional sensitivity analyses for AEs will be restricted to data collected prior rescue medication initiation.

An overall AE summary will be provided for the ST, ST+LT and randomised withdrawal periods, presenting the number and percentage of subjects by treatment group reporting at least 1 AE (excluding hypoglycaemic and DKA events that are not reported as SAEs) for the categories presented below. Incidence rates (as described in [Section 3.4.1](#)) adjusted for exposure time for ST+LT period might also be reported (as appropriate). The summary will be provided for both primary and sensitivity analyses for all treated subjects:

- At least one AE,
- At least one hypoglycaemia event,
- At least one AE or hypoglycaemia event,
- At least one SAE,
- At least one hypoglycaemia SAE,

- At least one adjudicated DKA SAE,
- At least one AE leading to discontinuation of study medication,
- At least one SAE leading to discontinuation of study medication,
- At least one hypoglycaemia SAE leading to discontinuation of study medication,
- At least one adjudicated DKA SAE leading to discontinuation of study medication,
- Deaths,
- At least one related AE,
- At least one related SAE,
- At least one AEOSI.

This analysis will be repeated for the combined ST+LT period up to Week 32 and also by treatment group received at the time of AE onset.

A weighted analysis for the overall AE summary will also be provided based on the ST+LT period, to account for the randomised withdrawal design (see Section 4.7 for details), and will include all data regardless of rescue medication initiation.

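### On the SAP's most coherent reading, a child who stops study drug for non-serious hypoglycaemia is in no adverse-event discontinuation count, and no named table links the episode to the stop

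*SAP*

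**What the plan says.** Protocol 3.7.3 foresees that study drug may be stopped for hypoglycaemia: "Clinical indications for discontinuation of blinded study drug because of hypoglycemia may include the following". The list that follows includes repeated symptoms and repeated glucose readings below 54 mg/dL, neither of which has to be serious.

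Protocol 5.3.1.2 then says where such a stop is recorded: "discontinuation due to hypoglycemia should not be reported on the AE eCRF page, unless the event fulfills protocol criteria for an SAE". SAP 3.4.3.2 repeats the rule for the event itself: "Hypoglycaemia event will not be reported on an AE CRF page unless the event fulfilled SAE criteria". SAP 3.4.1 sets the scope of adverse events to match: "AEs (serious and non-serious, excluding hypoglycaemic or DKA events that are not reported as SAEs) will be collected throughout the study".

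SAP 4.7.1.4 builds the discontinuation table from adverse events whose recorded action was permanent discontinuation of drug, and adds: "This summary will include all hypoglycaemia events and all DKA events that are reported as SAEs". In the overall AE summary (SAP 4.7.1.1) the only row joining hypoglycaemia to a stop is "At least one hypoglycaemia SAE leading to discontinuation of study medication".

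Outside the AE page, Protocol 3.7 requires this: "The reason for early discontinuation must be documented in the subject's medical records and entered on the appropriate CRF page".

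**The concern.** Discontinuations due to adverse events are a named safety endpoint (Protocol 8.3.3.4, SAP 3.4), and hypoglycaemia is named in the first safety objective (Protocol 1.3.3). Background insulin is allowed, and Protocol 1.4 reports that saxagliptin's hypoglycaemia rates were generally similar to placebo except with insulin or a sulfonylurea. Readers look to the AE discontinuation table for tolerability stops. If it omits stops for a key harm because the episodes were not serious, the table cannot show whether that harm drove children off treatment, and nothing in it would tell the reader so. SAP Section 6 lists an SAE-only restriction for DKA among the changes from protocol; it lists nothing comparable for hypoglycaemia.

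**Working it through.** The plan states no figure on this point, so the check is a trace of one case: a child on active drug has repeated non-serious hypoglycaemia and the investigator stops study drug.

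1. **AE page.** Not recorded there, under Protocol 5.3.1.2 and SAP 3.4.3.2.
2. **Overall AE summary (SAP 4.7.1.1).** The AE rows exclude hypoglycaemia not reported as an SAE. The episode counts in the row for any hypoglycaemia event and in the row for any AE or hypoglycaemia event, but neither concerns discontinuation. The rows for an SAE, and for a hypoglycaemia SAE, leading to discontinuation do not apply.
3. **SAE discontinuation summary (SAP 4.7.1.3).** Not counted; the event is not serious.
4. **AE discontinuation table (SAP 4.7.1.4).** The added sentence can be parsed in two ways. If the SAE condition governs both hypoglycaemia and DKA, the child is not counted. If it governs DKA only, all hypoglycaemia events are in scope and the child is counted. The first parse fits SAP 3.4.1 and 4.7.1.1. The second conflicts with them, and the SAP names no data source for it: its description of the hypoglycaemia page runs "Details include symptoms, contributing factors, blood glucose measurements during the episode, date and time of last meal, third party intervention, any treatment(s) received", then SAE status, with no mention of action taken with study drug.
5. **Hypoglycaemia section (SAP 4.7.2.4) and its rows in Table 24.** Episodes are tabulated by ADA and ISPAD category. No summary by discontinuation is specified.
6. **DKA, for comparison (SAP 4.7.2.2).** DKA is also kept off the AE page unless serious (SAP 3.4.3.1). Yet suspected DKA sent for adjudication has a leading-to-discontinuation summary for the combined short- and long-term period, with no restriction to SAEs.
7. **Disposition (SAP 4.2.1).** The child is counted as a treatment discontinuation, by arm and with a reason. The documents do not list the reason categories, so it cannot be seen whether hypoglycaemia would be identifiable.

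*Scale.* With about 81 children planned per arm, each uncounted child is 1/81 = 1.2 percentage points. Assuming purely for illustration one to three such children in an arm, the range is 1.2 to 3/81 = 3.7 points. The documents give no rate from which to choose a number.

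**The case against.** The strongest reply is that the plan reports hypoglycaemia apart from adverse events by design. The endpoint list names hypoglycaemic events and discontinuations due to AEs as separate items, so under the plan's own definition the discontinuation table matches its endpoint. That is fair as far as definitions go. But the same separation applies to DKA, where the SAP supplied the linking summary.

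A reader might infer that every such stop is lost, or that the tables would show hypoglycaemia causing no discontinuations. The documents do not support either inference:

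- The sentence in SAP 4.7.1.4 is ambiguous, as shown above.
- Protocol 6.3 sends to the AE forms any laboratory abnormality that required stopping drug, and Protocol 6.8.1 lists hypoglycaemic events among AEs of interest reported under the serious or nonserious rules. Both conflict with 5.3.1.2 and could bring some stops onto the AE page.
- SAP 4.7.2.4 summarises by arm everything collected on the hypoglycaemia pages, serious or not. If those pages hold an action-taken field, it would be covered. The CRF and table specifications are separate documents not available here. The SAP's description of the DKA page names no such field either, yet a DKA discontinuation summary is planned, so silence proves little.
- Disposition shows the stop and a reason.

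Frequency is also unknown. Protocol 3.7.3 says single episodes should not lead to stopping unless clinically indicated, and no insulin share is given. What survives is narrower: the rule followed as written leaves these stops out of the AE discontinuation counts, and no named output connects episode and stop.

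**Conclusion.** The point holds as a gap in planned reporting. On the reading consistent with Protocol 5.3.1.2 and SAP 3.4.1 and 4.7.1.1, a stop for non-serious hypoglycaemia is absent from the AE discontinuation table and from the discontinuation rows of the overall summary, and the hypoglycaemia section does not make up for it. This rests on two assumptions: that sites follow 5.3.1.2 rather than 6.3 or 6.8.1, and that the table specifications follow the SAE-only parse. The number of children affected cannot be derived, so no particular understatement of the discontinuation rate can be claimed. It merits correction because the harm is a named safety concern and the change is small.

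**What to change.** The change is to reporting and touches no rule on when treatment is stopped.

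- Reword the sentence in SAP 4.7.1.4 so that it says plainly which hypoglycaemia events it covers.
- Add a row for any hypoglycaemia event, serious or not, leading to discontinuation of study medication to the overall AE summary (4.7.1.1) and to 4.7.2.4, parallel to the DKA summary in 4.7.2.2. Show it beside the total in 4.7.1.4.
- Derive the row from the discontinuation reason on the disposition page or the early-treatment-discontinuation eCRF (Protocol 5.3.10.2), plus any action-taken field on the hypoglycaemia page. First confirm that these codes identify hypoglycaemia.
- Reconcile Protocol 6.3 and 6.8.1 with 5.3.1.2 on where hypoglycaemia is recorded.

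The cost is SAP wording and one derived flag, provided the reason codes are specific enough. The reported discontinuation count may be slightly higher.

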4.7.2 Other safety analyses

4.7.2.1 Amputation

All amputation events will be summarised for the ST+LT period. The number and proportion of subjects with amputation, type of event (trauma by accident, surgical amputation, spontaneous/non-surgical amputation), amputation lateral side, location of amputation, condition and underlying conditions that triggered amputation, and smoker status will be presented.

A listing of all amputation events will be provided for the ST+LT period.

4.7.2.2 Adjudicated Diabetic ketoacidosis (DKA)

All suspected DKA events sent for adjudication will be included in summaries for the ST, ST+LT and randomised withdrawal periods if their onset falls between the start of IP treatment and the cut-off dates defined for each period in [Table 8](#).

The proportion of subjects with suspected DKA events sent for adjudication, regardless of rescue medication initiation, will be tabulated by treatment group per adjudication category (definite DKA, probable DKA, possible DKA, not DKA) for the ST, ST+LT and randomised withdrawal periods. The proportion of subjects with suspected DKA events sent for adjudication leading to discontinuation per adjudication category will also be summarised for the ST+LT period. When summarising suspected DKA events leading to discontinuation of study medication, no upper cut-off day windows are applied.

Furthermore, suspected DKA events sent for adjudication will be summarised for the ST, ST+LT and randomised withdrawal periods by treatment group per adjudication category for number of subjects with each sign and symptom and separately, risk factors.

Suspected DKA events sent for adjudication will also be presented ST, ST+LT and randomised withdrawal periods by treatment group per adjudication category and preferred term. This analysis for the ST+LT period will be repeated for the subgroup of subjects on a stable baseline dose of metformin IR or XR (with or without insulin).

A listing of suspected DKA events sent for adjudication will be generated for adjudication results, signs and symptoms, and risk factors with an onset date/time from the start date/time for the ST+LT period. For the ST+LT + Week 104 period, the listing will include all data collected up to Week 104.

